A SBT is performed to evaluate a patient's ability to balance the respiratory load with their respiratory capacity. Factors that cause a load/capacity imbalance (e.g., increased  $R_{AW}$ , decreased lung compliance) often result in failed SBTs. Because of this, clinicians should ensure proper conditions when performing SBTs. Mucus buildup in the endotracheal tube, which results in luminal narrowing of the tube, can cause this load/capacity imbalance due to the increase in  $R_{AW}$ . Mietto et al noted that ETT luminal narrowing is common and can increase in airflow resistance. They noted that this narrowing occurred despite adequate humidification and suctioning. Wilson and colleagues studied the pressure drop across a sample of used ETTs and found that 33% of these tubes reflected an inner diameter change that matched an unused tube one size smaller. They also reported that in approximately 20-35% of patients, the change in pressure was greater than 5 cm H2O. Others have reported that endotracheal tube obstruction occurs more often than previously suspected and the onset can be as soon as 24 hours.

We previously studied the impact of ETT scraping on  $R_{AW}$  and found a statistically significant reduction. There is currently little to no data related to the frequency and impact of ETT scraping or sweeping on patient outcomes. However, we now use devices in our facility that have the ability to sweep ETTs; in addition to inline suction catheters (termed *standard* in this document) that cannot sweep ETTs. Thus, the primary aim of this study is to evaluate the CleanSweep™ Closed Suction System, which is used at Rush University Medical Center, on time to first successful SBT in mechanically ventilated patients in the medical intensive care unit. Secondary aims of this study are to evaluate the use endotracheal tube sweeping compared to closed suctioning effect on length of mechanical ventilation, length of ICU stay, length of total hospital stay, and occurrence of ventilator-associated events.

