## **Experimental Design and methods**

This is designed as a prospective, randomized control trial, in a large, urban, academic

medical center. This study will include mechanically ventilated patients (n = 272) in the medical intensive care unit (MICU) and adult intensive care unit at Rush University Medical Center. It will exclude patients with a tracheostomy on admission, those requiring extracorporeal membrane oxygenation (ECMO), or transferred from an outside facility receiving more than 24 hours of mechanical ventilation. Two groups will be randomly assigned via computer randomization. The comparison group will be placed on the CleanSweep™ Closed Suction System immediately after intubation or upon arrival to the MICU. ETTs will be cleaned with the balloon sweeping technology every time a respiratory therapist suctioning the patient. The standard group will be placed on the standard in-line suction device. Airway suctioning will be performed in both groups as per department policy (Catheter advanced until resistance is met and withdrawn slowly for a duration no longer than 15 seconds while applying negative pressure). Both groups will also receive a ventilator bundle that consists of head of bed elevation, ETT cuff pressure management, DVT prevention, daily sedation interruption and SBT, and oral care every 4 hours with chlorhexidine at 12pm (noon) and 12am midnight.

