### **Subject Population**

Two hundred and seventy-two orally intubated, adult patients  $\geq 18$  year of age will be enrolled.

Inclusion criteria:

- Age  $\geq 18$  y/o
- Orally intubated with endotracheal tube
- Mechanically ventilated  $< 24$  hours prior to enrollment

Exclusion criteria:

5.15.2020

- Age < 18 y/o
- Tracheostomy tube
- Extracorporeal membrane oxygenation
- Transfer from outside hospital with more than 24 hours of mechanical ventilation

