### **Plans for Data Analysis:**

- **Calculated sample size.** Based on previous institutional data, length of mechanical

ventilation is approximately 6.3 days with a standard deviation of 3.64. Effect is estimated at a 20% reduction in the length of mechanical ventilation ( $6.3 \times .20 = 1.26$  days). Standardized effect size would be 35% ( $1.26/3.64$ ). Setting alpha at 0.05 and power of .80 with standardized effect size of 0.35 would require 136 patients in each group or 272 total number of subjects. Estimated completion would be 18 to 24 months.

- Data for each patient will be recorded in REDCap, a secure web-based database. Descriptive and inferential statistics were calculated from the information collected from patients' charts. Patients were divided into two groups based on randomization. Each group's time to first successful SBT and length of mechanical ventilation outcomes will be compared using an independent T-test if the data is normally distributed. Ventilator-associated conditions and infection related ventilation associated complications rates for both groups will be compared using Chi-Square analysis. Level of significance will be set at  $p < 0.05$ .

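### Adjusting the two duration comparisons for a few covariates fixed in advance would be a cheap gain in precision; the planned unadjusted test is valid

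*Combined protocol and SAP*

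**What the plan says.** Plans for Data Analysis contains the whole analysis plan. Time to first successful SBT and length of mechanical ventilation "will be compared using an independent T-test", on condition that the data are normal. For ventilator-associated conditions and infection-related complications, "rates for both groups will be compared using Chi-Square analysis". No covariate, regression model, stratified test or adjusted sensitivity analysis is named.

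On allocation, Experimental Design and methods says "Two groups will be randomly assigned via computer randomization" and mentions no stratification, blocking or minimisation. The same section gives the setting as the "medical intensive care unit (MICU) and adult intensive care unit at Rush University Medical Center".

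Subject Population sets an age limit and restricts ventilation to under 24 "hours prior to enrollment", so age and prior hours on the ventilator must be known to establish eligibility. The data source is patients' charts, entered in REDCap ("Descriptive and inferential statistics were calculated from the information collected from" those charts). No section lists the baseline variables to be recorded.

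**The concern.** Patients in intensive care differ widely in how long they need the ventilator, and some of that difference is predictable at enrolment. The Introduction itself ties readiness to wean to the underlying disease, gas exchange, haemodynamic stability and mental status. A two-sample t-test leaves all predictable variation in the error term. A model that also includes baseline prognosis estimates the same mean difference with a smaller standard error, needs no extra patients and, with covariates fixed in advance, preserves type I error.

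At stake are some power and the width of the confidence interval. There is also a procedural benefit: if the arms happen to differ on an important baseline factor, the plan offers no agreed adjusted analysis, and one chosen after seeing the data would be open to challenge.

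**Working it through.** **Inputs from Plans for Data Analysis.** Mean length of ventilation 6.3 days, SD 3.64; effect 20%, so 6.3 × 0.20 = 1.26 days; alpha 0.05; power 0.80; 136 per group. Sidedness is not stated; I assume two-sided.

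**Reproducing the plan's figure.** The standardised effect is 1.26 / 3.64 = 0.346. A two-sided t-test at 80% power needs 132 per group, within 3% of the stated 136. With the effect rounded to 0.35 the t-test needs 130. Dividing the unrounded 129.1 by 3/π, the efficiency of the Wilcoxon test relative to the t-test under normality, gives 135.2, which rounds up to 136. The documents do not say which route was used, but the stated size is adequate for its inputs: at 136 per group and 1.26 days, power is 81.2%.

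**Effect of adjustment.** If covariates explain a share R² of the outcome variance:

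- residual SD = 3.64 × √(1 − R²)
- standardised effect = 0.346 / √(1 − R²)
- equivalent unadjusted size = 136 / (1 − R²) per arm

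The documents give no R², so a range is shown. Power is from the noncentral t distribution; the few degrees of freedom spent on covariates are ignored.

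| Assumed R² | Residual SD (days) | Power at 136 per arm | Equivalent unadjusted n per arm |
|---|---|---|---|
| 0 | 3.64 | 81.2% | 136 |
| 0.01 | 3.62 | 81.6% | 137 |
| 0.02 | 3.60 | 81.9% | 139 |
| 0.05 | 3.55 | 83.1% | 143 |
| 0.10 | 3.45 | 85.0% | 151 |
| 0.20 | 3.26 | 88.9% | 170 |

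Example at R² = 0.10: 3.64 × √0.90 = 3.45; 1.26 / 3.45 = 0.365; power 85.0%; 136 / 0.90 = 151.

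**Which covariates matter.** Eligibility guarantees only age and prior hours. If together they explain 1–2%, which is also an assumption, power rises by 0.4 to 0.8 points. Any larger gain has to come from severity and reason for intubation.

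**Scope.** The SD and effect are for length of ventilation. Specific Aims makes time to first successful SBT the primary outcome, and the documents give no SD or effect for it, so the table cannot be applied to it.

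**The case against.** The strongest reply is that nothing is wrong. The unadjusted comparison is unbiased, its standard error already allows for chance imbalance, and it exceeds its 80% power target on the plan's own inputs. All of that stands, and it is why this is offered as an improvement.

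Second, the useful covariates are not documented. That severity and reason for intubation can be found in the chart is a reasonable inference, but no section says so. This stands too: the upper rows of R² depend both on those variables being obtainable and on assumed values.

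Third, the linear-model gain applies only if the condition attached to the t-test is met. In a time-to-event model, adjustment changes the quantity estimated, because an adjusted hazard ratio is conditional on the covariates. This stands and is carried into the fix.

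A reader might infer three stronger things that the documents do not support:

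- **That chance imbalance biases the result.** It does not; it is part of the sampling error the t-test already counts. Quoting a possible shift in days alongside the power gain would count the same variance twice.
- **That tube size at enrolment is a mechanism-based covariate.** The Introduction says one study "found that 33% of these tubes reflected an inner diameter change that matched an unused tube one size smaller". That describes narrowing in tubes after use. It does not show that the size fitted at intubation predicts either outcome.
- **That randomisation is known to be unstratified.** The plan is silent; computer randomisation could include stratification.

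**Conclusion.** This is a cheap improvement to a valid analysis. The plan as written makes no use of baseline prognosis in the comparisons and states none in the allocation. For length of ventilation, a two-sided test of 1.26 days with SD 3.64 and 136 per arm would gain about 2, 4 or 8 points of power if covariates explained 5%, 10% or 20% of the variance, and under one point if they explained only 1–2%. The arithmetic is firm; the R² values are assumptions. The benefit for the primary outcome is likely to run in the same direction but cannot be sized from the documents. Nothing here shows the sample size of 272 to be wrong.

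**What to change.** Before any outcome data are examined, make the main comparison of time to first successful SBT and of length of ventilation a model of the outcome on randomised group plus a short fixed list of covariates:

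- age;
- hours ventilated before enrolment;
- unit (medical or adult ICU);
- reason for intubation, in categories defined in the plan;
- one severity score, named in the plan.

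All values should be from at or before randomisation. For the severity score this must be written down, since a score abstracted later from the chart could take in values recorded after the device was in place. State also how a missing baseline value will be handled.

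Report the adjusted difference with its 95% confidence interval and keep the unadjusted test as a sensitivity analysis. Use the same covariates in whatever model is adopted for each outcome; if it is non-linear or time-to-event, say that the adjusted effect is conditional on them. If allocation was in fact stratified, say so and include the stratification factors. The chi-square comparisons can stay as planned.

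The cost is a sentence or two in the plan, a few baseline REDCap fields, minor chart abstraction and occasional missing values. It needs no extra patients and no change to treatment.
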